Lorincz et al [6] used a genetic analysis of a CTX patient with German-English ancestry with consanguineous parents (second cousins) and her family members to estimate the prevalence of CTX. Molecular genetic analysis was performed using DNA extracted from peripheral blood leukocytes of the patient, her family members, and 115 white volunteer controls of European ancestry. The CYP27A1 exon from each sample was amplified by polymerase chain reaction. Sequencing of the amplified DNA resulted in the identification of a single homozygous substitution of thymidine for cytosine at complementary DNA position 1384 for the patient. Sequence analysis of DNA from both parents showed that they were both heterozygous, cytosine/ thymidine, at the same position. Unexpectedly, one control patient who was heterozygous for the same mutation at position 1384 was identified. Haplotype analysis of DNA from the heterozygous control patient was not performed, but there was no known familial relationship to the patient. The observed frequency of the mutation calculated for the control group was 8.7×10^{-3} . The prevalence of CTX due to this one homozygous mutation was

estimated at 1.9 per 100,000. The overall prevalence of CTX due to all known mutations was estimated to be “several-fold” higher, approximately 3 to 5 per 100,000.

Pilo-de-la-Fuente et al [7] reported on data for all patients diagnosed with CTX between 1992 and 2008 at any of the main reference centers for genetic diagnosis of CTX in Spain. CTX diagnosis was based on clinical features and mutational analysis with one exception, a patient diagnosed in 1992 for whom DNA was not available. Twenty-five CTX patients, from 19 families were identified. The authors estimated a minimum prevalence of 1/1,800,000 individuals in Spain.

Diagnosis of cerebrotendinous xanthomatosis

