Suspicion of CTX is typically based on clinical symptoms, most often including chronic diarrhea with infantile onset, bilateral cataracts in children, and the appearance of xanthomas on the Achilles tendons, extensor tendons of the elbows and hands or patellar tendons, often by the third decade of life.[8] Biochemical abnormalities that indicate likely CTX are elevated bile and plasma cholestanol levels, increased ratio of serum cholestanol/cholesterol, increased urinary excretion of bile alcohol glucuronides and diminished biliary concentrations of chenodeoxycholic acid (CDCA).[9, 10] In clinical practice, elevated plasma cholestanol and urine bile alcohol are used as tests for probable CTX, with the diagnosis confirmed by a finding of mutation in the *CY 27A1* gene on chromosome 2q35-qter.[8, 11]

Treatment of cerebrotendinous xanthomatosis

CDCA has long been considered to be the standard of care for the condition. CDCA treatment is effective in preventing adverse clinical manifestations of the disease from occurring or progressing if the treatment is administered early enough.[12] Though the extent of published evidence is limited, available clinical studies and case reports suggest that the ability of CDCA treatment to reverse existing adverse clinical manifestations is mixed, with some manifestations being at least partially reversed and others stabilizing. Initiation of CDCA treatment as early as possible is universally recommended by experts, before irreversible damage has occurred.[13] There are also published reports of cholic acid being used instead of CDCA.[14, 15, 27] Recently, cholic acid has been approved for the treatment of bile acid synthesis disorders, including CTX [27].

Other treatments that have been reported to be combined with CDCA treatment in clinical practice are: Vitamin D, Vitamin E, anti-seizure medications, L-dopa-carbidopa, anti-psychotic medications, anxiolytics, anti-depressants and statins.[16-23] In a small number of reported

cases, statins were given without CDCA.[22, 24] Apheresis treatment has also reported in a small number of cases, in combination with CDCA or alone.[7, 25, 26]

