2.2 Endpoints

- Proportion of patients with positive CTX test based on
 - Elevated plasma cholestanol level ≥ 0.4 mg/dL (4 μ g/mL) or
 - Positive urine bile alcohol results among those with urine sample
- Proportion of patients with confirmed CTX based on genetic testing for mutations associated with CTX among those with non-missing plasma cholestanol or urine bile alcohol results
- Proportion of patients with confirmed CTX based on genetic testing for mutations associated with CTX among those with elevated plasma cholestanol levels or positive urine bile alcohol results
- Plasma cholestanol, plasma cholesterol, and urine bile alcohol levels

- Incidence of serious adverse events (SAEs) associated with study procedures (i.e. a blood draw)

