5.7 CTX Testing Analyses

Results of CTX testing (plasma cholestanol, plasma cholesterol, urine bile alcohol, and genetic testing) will be summarized using the Enrolled Set when data are available.

Summary statistics (n, mean, median, standard deviation, minimum, and maximum) will be reported for continuous variables. Frequency counts and percentages will be reported for categorical variables. A listing of CTX testing data will also be provided.

Additionally, the prevalence of CTX will be examined on the basis of the following percentages, reported together with 95% confidence intervals:

1. Patients with a plasma cholestanol level ≥ 0.4 mg/dL (4 μ g/mL).
2. Patients with a positive test for urine bile alcohol.
3. Patients with a plasma cholestanol level ≥ 0.4 mg/dL (4 μ g/mL) or a positive test for urine bile alcohol.
4. Patients with a positive genetic test for CTX.
5. Patients with a positive genetic test for CTX among those with elevated plasma cholestanol level or positive urine bile alcohol result.

For criteria 1 and 2, denominator of the percentage will be based on the number of patients with non-missing results. For criteria 3 and 4, denominator of the percentage will be based on the number of patients with either plasma cholestanol or urine bile alcohol results reported. Two-sided 95% confidence intervals will be calculated using the exact Clopper-Pearson method.

SAS® sample code for the Clopper-Pearson method:

```
data clop_ci;
set lb;
p=round ((x/n), .001);
if p=0 then CI_LOW=0;
if p=1 then CI_HIGH=1;
if p ne 0 then CI_LOW=round((1-betainv(.975, (n-x+1), x)), .00001);
if p ne 1 then CI_HIGH=round((1-betainv(.025, (n-x), x+1)), .00001);
run;
```

Table 1 lists the mapped genetic testing results that will be used for summary.

Table 1: Genetic Testing Results

Mapped Genetic Testing Result	Reported Genetic Testing Result
Positive	Positive
	Likely positive
Negative	Inconclusive
	Negative
	No mutations identified
	No biochemical evidence of CTX
	No mutations were identified
	No mutations found

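### Screen-positive patients with a missing or inconclusive genetic result enter the CTX prevalence estimate as non-cases, and the prevalence table does not show how many there are

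*SAP*

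**What the plan says.** The primary objective is to calculate the prevalence of CTX. The SAP figure closest to it is criterion 4 in SAP 5.7. Its numerator is patients with a positive genetic test. For its denominator, the "denominator of the percentage will be based on the number of patients with either plasma cholestanol or urine bile alcohol results reported". SAP 2.2 defines the same endpoint as the proportion with "confirmed CTX based on genetic testing for mutations associated with CTX among those with non-missing plasma cholestanol or urine bile alcohol results".

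Only patients with raised cholestanol or positive urine bile alcohol (screen-positives) go on to genetic testing (Protocol 5.1.3 and 8.5). SAP 5.7 then recodes what the laboratory reports: "Table 1 lists the mapped genetic testing results that will be used for summary". In that table *Likely positive* becomes *Positive*, and *Inconclusive* becomes *Negative*.

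Criterion 5 is "Patients with a positive genetic test for CTX among those with elevated plasma cholestanol level or positive urine bile alcohol result", and SAP 2.2 gives the same population: "confirmed CTX based on genetic testing for mutations associated with CTX among those with elevated plasma cholestanol levels or positive urine bile alcohol results".

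SAP 4.4 leaves missing data missing and gives no rule for a screen-positive patient who has no genetic result. No sensitivity analysis is planned. SAP section 8, Table 2 plans separate *CTX Testing Results* and *Prevalence of CTX* tables, both on the Enrolled Set, and a listing of CTX testing results.

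**The concern.** The protocol's Introduction says that "elevated plasma cholestanol and urine bile alcohol are used as tests for probable CTX, with the diagnosis confirmed by a finding of mutation". A screen-positive patient without a conclusive genetic result is therefore unconfirmed, not shown to be free of CTX. Under the SAP that patient adds 1 to the criterion 4 denominator and 0 to the numerator, exactly as a genetic negative does. Unresolved patients all come from the group most likely to have the disease, so this treatment can only lower the estimate.

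The two routes differ in how they arise and in how visible they are.

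- **Missing result.** This follows from the denominator definition and is not a separately stated rule. Withdrawal (Protocol 5.2.2.2) or early termination of a site or the study (Protocol 12.4.5) could cause it.
- **Inconclusive result.** The test was done, and Table 1 explicitly recodes the result. The protocol's safeguards aim to get each indicated test done. They allow a replacement blood sample but do not require a repeat after an inconclusive result.

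At stake is how the headline figure is read. The criterion 4 percentage and interval look the same whether no screen-positive patient is unresolved or several are. If there are few confirmed cases, one unresolved patient is large relative to the numerator.

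**Working it through.** **Inputs.** Planned enrolment is about 500 (SAP 4.6). The interval is two-sided 95% Clopper-Pearson (SAP 5.7). The documents state no expected prevalence in cataract patients, no screen-positive rate and no unresolved rate, so there is no plan figure to reproduce. The population estimates in the protocol's Introduction, such as "approximately 3 to 5 per 100,000", do not carry over to patients selected for bilateral cataracts. The following are therefore assumptions: N = 500 patients with a biomarker result, x = 0 to 5 genetic positives, u = 1 to 7 unresolved screen-positives, and S = 20 or 50 screen-positives in all.

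**Step 1: the planned figure.** The estimate is x/N. The limits are 1 − BetaInv(0.975; N−x+1, x) and 1 − BetaInv(0.025; N−x, x+1), with a lower limit of 0 when x = 0. For x = 3, 3/500 = 0.60%, with limits 0.124% and 1.743%. Neither the estimate nor the limits depend on u.

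**Step 2: worst case.** If every unresolved patient has CTX, the sample figure is (x+u)/N. Each unresolved patient adds 1/500 = 0.20 points.

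| x | Reported (95% CI) | u = 1 | u = 2 | u = 5 | Smallest u with (x+u)/N above the reported upper limit |
|---|---|---|---|---|---|
| 0 | 0.00% (0 to 0.735) | 0.20% | 0.40% | 1.00% | 4 (0.80%) |
| 1 | 0.20% (0.005 to 1.109) | 0.40% | 0.60% | 1.20% | 5 (1.20%) |
| 2 | 0.40% (0.048 to 1.437) | 0.60% | 0.80% | 1.40% | 6 (1.60%) |
| 3 | 0.60% (0.124 to 1.743) | 0.80% | 1.00% | 1.60% | 6 (1.80%) |
| 5 | 1.00% (0.325 to 2.318) | 1.20% | 1.40% | 2.00% | 7 (2.40%) |

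The worst-case figure for x = 3 and u = 2 is 5/500 = 1.00%, with its own interval 0.325% to 2.318%.

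**Step 3: a less extreme case.** Suppose unresolved patients are positive at the same rate as conclusive ones, x/(S−u). The added prevalence is u × x/(S−u)/N. With x = 3:

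- S = 50, u = 2: 2 × 3/48 = 0.125 cases, or 0.025 points.
- S = 20, u = 2: 2 × 3/18 = 0.333 cases, or 0.067 points.
- S = 50, u = 5: 5 × 3/45 = 0.333 cases, or 0.067 points.
- S = 20, u = 5: 5 × 3/15 = 1 case, or 0.20 points.

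**Step 4: does dropping the unresolved help?** No. 3/498 = 0.602% against 3/500 = 0.600%. The denominator is mostly screen-negatives, so removing two patients barely changes it.

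**Step 5: what the other planned outputs show.** The criterion 3 numerator minus the number with a genetic result in the *CTX Testing Results* table gives the missing count. Both are on the Enrolled Set, and the subtraction assumes that only screen-positives are tested. An inconclusive result counts there as a result and appears as *Negative*. Only the listing could reveal it, and the SAP does not say whether the listing gives reported or mapped results.

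**Step 6: the opposite direction.** If one of 3 counted positives were *Likely positive*, a count of *Positive* results alone would give 2/500 = 0.40% (0.048% to 1.437%).

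**Step 7: criterion 5.** With x = 3 and u = 2, all screen-positives against conclusive results only gives 3/50 = 6.0% against 3/48 = 6.25%, or 3/20 = 15.0% against 3/18 = 16.7%.

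**The case against.** The best reply is that the endpoint is *confirmed* CTX. An unresolved patient is not confirmed, so leaving that patient out of the numerator follows SAP 2.2, and the denominator and the mapping are both stated openly. This stands as far as it goes: criterion 4 does what it says, and the fix keeps it as the main figure. It does not remove the gap, because the same figure serves as the prevalence estimate and its row does not show how many patients remain unconfirmed.

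The protocol also aims for no unresolved results. All screen-positives are to be tested (5.1.3), replacement samples are allowed (5.2.2.1), completion requires testing to be recorded for all patients (5.2.2.3), and blood for genetic testing is drawn at enrolment (Appendix Table 1). That stands, and it is why the effect may be zero.

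A reader might infer more than the documents support:

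- *Missing results cannot be found.* They can be derived on the Enrolled Set (Step 5). Only inconclusive results are hidden in the summary tables.
- *The criterion 5 denominator is ambiguous*, because results "will be summarized using the Enrolled Set when data are available". That phrase belongs to the descriptive summaries. The percentages are introduced separately, and SAP 2.2 states their population.
- *The no-imputation rule in SAP 4.4 is broken.* It is not, since no value is assigned to a missing result.
- *Criterion 4 is a lower bound.* It is not, because *Likely positive* is counted as *Positive*.
- *The confidence interval fails.* For 1 to 3 unresolved patients and 0 to 5 positives, even the worst case stays inside it.

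**Conclusion.** The point holds as a minor reporting weakness. Unresolved screen-positives count as non-cases in the prevalence estimate, by the explicit mapping if inconclusive and by the denominator definition if missing. The prevalence table does not disclose them.

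The effect is zero if all indicated tests are resolved. Otherwise it is at most 0.20 points per unresolved patient at N = 500. For 3 positives and 2 unresolved, that is 0.60% reported against 1.00% at worst, and about 0.63% to 0.67% if unresolved patients resemble conclusive ones. The worst case leaves the reported interval only from 4 unresolved (0 positives) up to 7 unresolved (5 positives). Apart from the planned N, all these counts are assumptions, and inconclusive results may not resemble conclusive ones.

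**What to change.** In SAP 5.7:

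1. Show in the prevalence table, as separate counts, the screen-positives with a missing genetic result, those with an inconclusive result, and the *Likely positive* results counted as *Positive*.
2. If any result is unresolved, keep x/N as the main criterion 4 figure, labelled *unresolved counted as negative*. Add (x+u)/N with its Clopper-Pearson interval, labelled as a worst-case sensitivity row and not an imputation, so that SAP 4.4 stands. If any result is *Likely positive*, add a row counting only *Positive* results, so that the range covers both directions.
3. Keep all screen-positives as the criterion 5 denominator, as SAP 2.2 states, and show the percentage among conclusive results beside it.

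Table 1 can keep its mapping for the main figures. The cost is a few sentences of SAP text and two or three extra rows, with no new data or modelling. The downside is a less tidy headline when results are unresolved. If none are unresolved, the zero counts tell the reader that the genetic testing behind the headline is complete.

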6 SAFETY ANALYSIS

Safety analysis will be based on the Safety Set. The only planned safety analysis is procedure-related or possibly related AEs.

6.1 Adverse Events

An AE is any untoward medical occurrence associated with the performance of a study procedure in a clinical investigation patient. A procedure-related AE is an AE occurring during a clinical study that is considered by the investigator or the medical monitor (or designee) to be related to a research procedure. For example, a procedure-related AE may be an untoward event related to a medical procedure required by the protocol (i.e. a blood draw in the case of this study).

Only SAEs determined by the investigator to be possibly related or related to study procedures are planned to be recorded for this study; however, all procedure-related or possibly related AEs will be analyzed if collected. All AEs will be coded using MedDRA version 24.0.

An overall summary of procedure-related or possibly related AEs will be provided, which includes:

- The number and percentage of patients experiencing a procedure-related or possibly related AE;
- The number and percentage of patients experiencing a procedure-related or possibly related AE by greatest severity;
- The number and percentage of patients experiencing a procedure-related or possibly related AE leading to study withdrawal;
- The number and percentage of patients experiencing a procedure-related or possibly related AE resulting in death.

Additionally, the number and percentage of patients experiencing a procedure-related or possibly related AE will be summarized by SOC and PT.

Data of procedure-related or possibly related AEs will also be listed.

7 CHANGES TO THE PLANNED ANALYSES FROM THE PREVIOUS SAP

The current SAP is based on the study protocol amendment 2, dated 13DEC2016; whereas the previous SAP (version 1.0, dated 26FEB2016) uses the protocol amendment 1, dated 08JUL2015.

While study endpoints and general statistical methods stay the same between the two versions of SAP, more details have been added on both in the current version, and updates have been made to reflect the changes in the latest protocol. Appendix **Error! Reference source not found.** provides a summary of key changes to the planned analyses from the previous SAP.

8 TABLE OF CONTENT (TOC) FOR OUTPUTS

Table 2: TOC for Tables and Listings

Output Type	Output Name	Analysis Set
Table	Analysis Sets	Screened Set
Table	Patient Disposition	Screened Set
Table	Demographics and Baseline Characteristics	Enrolled Set
Table	CTX Medical History	Enrolled Set
Table	Concomitant Medications	Enrolled Set
Table	CTX Testing Results	Enrolled Set
Table	Prevalence of CTX	Enrolled Set
Table	Overall Summary of Procedure-related or possibly related AEs	Safety Set
Table	Procedure-related or possibly related AEs by SOC and PT	Safety Set
Listing	Analysis Sets	Screened Set
Listing	Subject Eligibility	Screened Set
Listing	Patient Disposition	Screened Set
Listing	Demographics and Baseline Characteristics	Enrolled Set
Listing	CTX Medical History	Enrolled Set
Listing	Family History	Enrolled Set
Listing	Concomitant Medications	Enrolled Set
Listing	CTX Testing Results	Enrolled Set

Listing	Procedure-related or possibly related AEs	Safety Set
---------	---	------------

9 APPENDIX

9.1 Schedule of Events

	Screening/Enrollment	CTX Testing (if Necessary)
Confirm Study Eligibility	X	
Obtain Informed Consent	X	
Demographics	X	
Targeted Medical History ¹	X	
Concomitant Medications/Therapies ²	X	
Blood draw for Plasma Cholestanol testing and Genetic testing ³	X	
Urine collection for Bile Alcohol testing (if urine sample is provided) ⁴	X	
Serious Adverse Events related to procedures	X	
Genetic Testing for CTX ⁵		X
Photographic Documentation of Cataracts ⁶		X
Follow-Up Notification of Results	X ⁷	X ⁸
Study Discontinuation	X ⁷	X ⁸

¹ History of or current manifestations of signs and symptoms commonly associated with CTX.

² Concomitant medications and therapies during the week prior to enrollment will be collected.

³ Blood draw may be collected in conjunction with other scheduled treatments during medical care that is separate from the clinical study.

⁴ Urine sample (if provided) may be collected in conjunction with other scheduled treatments during medical care that is separate from the clinical study.

⁵ Will be completed if patient plasma cholestanol level is ≥ 0.4 mg/dL (4 μ g/mL) or urine bile alcohol is positive (if urine sample is provided).

⁶ If available, collected for patients who have been diagnosed with CTX.

⁷ For those patients with *normal results* for plasma cholestanol <0.4 mg/dL (4 μ g/mL) and urine bile alcohol is negative (if urine sample is provided), participation ends after tests results have been communicated to the patient and study discontinuation page is completed.

⁸ For those patients who *require genetic testing*, participation ends after reporting of test results to the patient, and study discontinuation page is completed.

9.2 Key Changes to the Planned Analyses from the Previous SAP

Section	SAP Version 1.0	Current SAP
Primary Objective	Patient population diagnosed up to age 21	Patient population diagnosed between the ages of 2 and 21 years old (inclusive)
Other Endpoints	CTX testing will be done using plasma cholestanol and urine bile alcohol levels (if urine sample is provided) for all study participants. Genetic testing for mutations associated with CTX will be done for all study participants with elevated plasma cholestanol levels or positive urine bile alcohol results (if urine sample is provided).	
• Proportion of patients with positive CTX test based on
○ Elevated plasma cholestanol level ≥ 0.4 mg/dL (4 μg/mL) or○ Positive urine bile alcohol results among those with urine sample• Proportion of patients with confirmed CTX based on genetic testing for mutations associated with CTX among those with non-missing plasma cholestanol or urine bile alcohol results.• Proportion of patients with confirmed CTX based on genetic testing for mutations associated with CTX among those with elevated plasma cholestanol levels or positive urine bile alcohol results.• Plasma cholestanol, plasma cholesterol, and urine bile alcohol levels.
Study Design	Participation in the study is limited to one clinic visit.	Participation in the study is limited to one or more study visit(s) for collection of study data, including a blood draw

		and urine sample (if provided). These procedures will typically be completed in a single visit, but additional visits are permitted if a blood sample is not obtained or a replacement blood sample is required for any reason.
General Considerations for Data Analysis	No description on the precision of the summary	Minimum and maximum values will be presented to the precision of the original value. Means and medians will be rounded to one decimal place greater than the precision of the original value. Standard deviation and 95% confidence intervals will be rounded to two decimal places greater than the precision of the original value. Percentages for summarizing categorical data will be rounded to one decimal place.
Analyses Sets	All patients will be included in the analysis dataset. All study patients who undergo invasive study procedures (i.e. a single blood draw) will be included in the safety dataset.	All patients who signed the informed consent will be included in the Screened Set. All patients who signed the informed consent and whose eligibility was established will be included in the Enrolled Set. All enrolled patients who undergo invasive study procedures (i.e. a blood draw) will be included in the Safety Set.
Handling of Multiple Lab Observations	No description	If multiple lab records exist at a collection time point, the repeated record will be used for data summary.
Analysis Sets	No description	The number and percentage of patients in each analysis set will be summarized. The data will also be listed.

Subject Eligibility	No description	Subject eligibility for the study (inclusion and exclusion criteria failures) will be listed for the Screened Set.
Disposition of Patients	
A table of counts of all safety patients who complete the study will be provided.
 
Reasons for not completing study as planned will be tabulated. A patient listing for early discontinuations and reasons for discontinuation will be provided for the safety analysis set.
 
The number of patients with evaluable CTX testing data based on plasma cholestanol levels, urine bile alcohol levels, and genetic testing will also be summarized.
	
Patient disposition will be presented for the Enrolled Set. The number and percentage of patients who complete or discontinue the study, as well as the discontinuation reasons, will be provided. In addition, the number of patients who have plasma samples, urine samples, or genetic tests will be summarized.
 
A patient listing for study disposition will be provided for the Enrolled Set.

Demographics and Baseline Characteristics	Demographics and baseline characteristics (age/age categories, sex, race, ethnicity, and baseline characteristics) will be analyzed using the safety analysis set.	Demographics and baseline characteristics (age, sex, race, and ethnicity) will be analyzed using the Enrolled Set.
Medical History	A targeted CTX specific medical history will be collected for all patients enrolled in the study. It includes any history of or current manifestation of signs and symptoms commonly associated with CTX. Medical history terms will not be coded. Information collected from the targeted CTX specific	A targeted medical history is collected for all patients enrolled in the study. It includes any history of, or current manifestation of, signs and symptoms commonly associated with CTX. Medical history terms will be coded using the Medical Dictionary for Regulatory Activities (MedDRA) version 24.0. The number and percentage of patients with each medical condition will be summarized

	
medical history such as, ophthalmological disorders other than cataracts, xanthomas, etc. will be summarized in the same fashion as the demographics. Should coding of medical history term be required at a later date, all medical conditions and surgical procedures will be classified by system organ class (SOC) and preferred term (PT) using the Medical Dictionary for Regulatory Activities (MedDRA) version 18.1 (or higher). The number and percent of patients with each medical condition and surgical procedure will be presented for each SOC and PT for the safety analyses set.
 
All medical history data will also be listed.
	
by System Organ Class (SOC) and Preferred Term (PT) for the Enrolled Set.
 
All medical history data (including family history) will be listed.

Prior and Concomitant Medications	
Concomitant medications and therapies the patient has taken in the week prior to enrollment will be recorded during the single study visit. Concomitant medications will be coded using World Health Organization (WHO) drug classifications. The number and percent of safety patients using concomitant medications will be tabulated by drug class and by preferred name using the safety analysis set. All prior and concomitant medication data will be listed, sorted by investigative site and patient number, start
	
Concomitant medications and therapies the patient has taken in the week prior to enrollment will be recorded during the study visit(s). Concomitant medications will be coded using WHODrug Global B3 released in March 2021. Each verbatim term will be classified by anatomical main group (ATC level 1), therapeutic subgroup (ATC level 2), pharmacological subgroup (ATC level 3), chemical subgroup (ATC level 4), and chemical substance (ATC level 5).

	
and stop date. Information listed will include medication, indication, dose, unit, frequency and route of administration.
	
The number and percentage of patients using concomitant medications will be summarized by ATC level 2 and preferred term using the Enrolled Set.
 
All prior and concomitant medication data will also be listed.

CTX Testing Analyses	
Results of CTX testing (plasma cholestanol level, urine bile alcohol results (if urine sample is provided), and genetic testing) will be summarized using all patients with evaluable data for each assessment. Summary statistics (n, mean, median, standard deviation, minimum, and maximum) will be reported for continuous variables. Frequency counts and percentages will be reported for categorical variables. A listing of CTX testing data will also be provided.
 
Specifically, the prevalence of CTX will be examined on the basis of the following percentages, reported together with 95% confidence intervals:
 
1. Patients with a plasma cholestanol level ≥ 0.4 mg/dL (4 mcg/mL).2. Patients with a plasma cholestanol level ≥ 0.4 mg/dL (4 mcg/mL) and a positive test for urine bile alcohol.	
Results of CTX testing (plasma cholestanol, plasma cholesterol, urine bile alcohol, and genetic testing) will be summarized using the Enrolled Set when data are available. Summary statistics (n, mean, median, standard deviation, minimum, and maximum) will be reported for continuous variables. Frequency counts and percentages will be reported for categorical variables. A listing of CTX testing data will also be provided.
 
Additionally, the prevalence of CTX will be examined on the basis of the following percentages, reported together with 95% confidence intervals:
 
1. Patients with a plasma cholestanol level ≥ 0.4 mg/dL (4 μg/mL).2. Patients with a positive test for urine bile alcohol.3. Patients with a plasma cholestanol level ≥ 0.4 mg/dL (4 μg/mL) or a positive test for urine bile alcohol.4. Patients with a positive genetic test for CTX.

	
3. Patients with a plasma cholestanol level ≥ 0.4 mg/dL (4 mcg/mL), a positive test for urine bile alcohol, and a positive genetic test for CTX.
 
Two-sided 95% confidence intervals will be calculated using the Newcombe-Wilson score method.
	
5. Patients with a positive genetic test for CTX among those with elevated plasma cholestanol level or positive urine bile alcohol result.
 
For criteria 1 and 2, denominator of the percentage will be based on the number of patients with non-missing results. For criteria 3 and 4, denominator of the percentage will be based on the number of patients with either plasma cholestanol or urine bile alcohol results reported. Two-sided 95% confidence intervals will be calculated using the exact Clopper-Pearson method.
 
SAS® sample code for the Clopper-Pearson method:
 <pre>data clop_ci; set lb; p=round ((x/n), .001); if p=0 then CI_LOW=0; if p=1 then CI_HIGH=1; if p ne 0 then CI_LOW=round((1-betainv(.975, (n-x+1), x)), .00001); if p ne 1 then CI_HIGH=round((1-betainv(.025, (n-x), x+1)), .00001); run;</pre> 
Table 1 lists the mapped genetic testing results that will be used for summary.

--	--	---
